STUDY PROTOCOL

PASS Information

Title	EURAS-CORA European Active Surveillance Study Comparing Regimens of Application in combined hormonal contraception
Protocol version identifier	ZEG2014_03
Date of last version of protocol	01 August 2014
EU PAS register number	Study not yet been registered
Active substance	Pharmacotherapeutic group: Sex hormones and modulators of the genital system, progestogens and estrogens, fixed combinations ATC code: G03AA 1 0 gestodene and estrogen Active substances: gestodene and ethinyl estradiol
Medicinal product	apleek ¹ : transdermal patch releasing 60 micrograms gestodene/24 hours + 13 micrograms ethinyl estradiol/24 hours
Product reference	
Procedure number	FR/H/0547/001/DC
Marketing authorisation holder(s)	Bayer HealthCare Pharmaceuticals [name]
Joint PASS	No
Research question and objectives	Primary objective: characterization and comparison of the risks of short- and long-term use of FC Patch Low with COC _{LNG} . Main clinical outcomes of interest: venous thromboembolism, specifically deep venous thrombosis of the lower extremities and pulmonary embolism.
Country(-ies) of study	Approximately 6 European countries (tbd)
Author	[name], PhD, MBA, MSc [name] [contact] [contact]

¹ Throughout the study protocol, the term „FC Patch Low“ will be used for the product name “apleek”

Marketing authorisation holder(s)

Marketing authorisation holder(s)	Bayer HealthCare Pharmaceuticals [name]
MAH contact person	[name], PhD Senior GMA Physician PASS Bayer HealthCare Pharmaceuticals [name] [contact] [contact]

1 Table of Contents

1	Table of Contents	3
2	List of Abbreviations	5
3	Responsible Parties	8
4	Abstract	9
5	Amendments and updates	12
6	Milestones	12
7	Rationale and background	13
8	Research question and objectives	15
9	Research methods	16
9.1	Study design	16
9.2	Setting	17
9.2.1	Treatments	17
9.2.2	Selection of Study Population	17
9.2.3	Baseline Survey	18
9.2.4	Follow-Up Phase	19
9.2.5	Validation of Self-Reported Events	20
9.2.6	Loss to follow-up	21
9.3	Variables	22
9.3.1	Primary Endpoint	22
9.3.2	Secondary Endpoints	23
9.4	Data sources	23
9.5	Study size	25
9.6	Data management	26
9.6.1	Databases	26
9.6.2	Dataflow	27
9.6.3	Database Freeze/Lock	27
9.7	Data analysis	28
9.8	Quality control	30
9.9	Limitations of the research methods	31
9.10	Other aspects	32
9.10.1	Validation of self-reported events	32
9.10.2	Blinded adjudication	35
9.10.3	Drug relationship	36
10	Protection of human subjects	37
10.1	Institutional Review	37
10.2	Informed Consent	37
10.3	Safety Monitoring and Advisory Council	38
11	Management and reporting of adverse events/adverse reactions	38
12	Plans for disseminating and communicating study results	39
13	References	40
	Annex 1. List of stand-alone documents	42
	Annex 2. ENCePP checklist for study protocols	43

Annex 3. Additional information..... 49

2 List of Abbreviations

Abbreviation	Definition
ADB	Administrative Database
AE	Adverse Event
AMI	Acute Myocardial Infarction
AT	As Treated
ATC	Anatomical Therapeutic Chemical Classification System
ATE	Arterial Thromboembolism
BMI	Body Mass Index
CHC	Combined Hormonal Contraceptive
CHMP	Committee for Medical Products for Human Use
COC	Combined Oral Contraceptive
COC _{LNG}	Levonorgestrel-containing COC
CT	Computer Tomography
CVA	Cerebrovascular Accidents
DCP	Decentralized Procedure
DIMDI	German Institute for Medical Documentation and Information
DVT	Deep Venous Thrombosis
ECG	Electrocardiogram
EE	Ethinyl Estradiol
EMA	European Medicines Agency
ENCePP	European Network of Centres for Pharmacoepidemiology and Pharmacovigilance
EU	European Union
EURAS	European Active Surveillance (study)
FC	Fertility Control
GEP	Good Epidemiological Practices
GPP	Good Pharmacoepidemiology Practices
GSD	Gestodene
GVP	Good Pharmacovigilance Practice

GXP	Good Practice Guidelines
HC	Hormonal Contraceptive
HR	Hazard Ratio
ICD-10	International Classification of Diseases, 10th revision
ICMJE	International Committee on Medical Journal Editors
INAS	International Active Surveillance Study
ITT	Intention To Treat
LNG	Levonorgestrel
MAH	Marketing Authorization Holder
MRI/MRT	Magnetic Resonance Image/-Tomography
NGMN	Norelgestromin
OC	Oral Contraceptive
OPS	Operations and Procedures Classification System (acronym for the German term 'Operationen- und Prozedurenschlüssel')
PASS	Post-Authorization Safety Study
PE	Pulmonary Embolism
PIP	Pediatric Investigation Plan
PMDD	Premenstrual Dysphoric Disorder
PMS	Premenstrual Syndrome
PRAC	Pharmacovigilance Risk Assessment Committee
RMP	Risk Management Plan
SAE	Serious Adverse Event
SDB	Study Database
SMAC	Safety Monitoring and Advisory Council
SOP	Standard Operating Procedure
TASC	Transatlantic Active Surveillance on Cardiovascular Safety of NuvaRing
TIA	Transient ischemic attack
VTE	Venous Thromboembolism
WHO	World Health Organization
WY	Woman-years

ZEG Berlin Center for Epidemiology & Health Research (acronym for the German term 'Zentrum für Epidemiologie & Gesundheitsforschung Berlin')

3 Responsible Parties

PRINCIPAL INVESTIGATOR:	[name] [name] Email: [contact]
STUDY CONDUCT:	ZEG – Berlin Center for Epidemiology and Health Research [name]
PROJECT MANAGER:	[name] ZEG – Berlin Center for Epidemiology and Health Research [name] Email: [contact]
FUNDER:	Bayer HealthCare Pharmaceuticals (hereafter referred to as the FUNDER) [name]
FUNDER CONTACT INFORMATION:	[name] Senior GMA Physician PASS Bayer HealthCare Pharmaceuticals [name] [contact] [contact]
SAFETY MONITORING AND ADVISORY COUNCIL:	Members: tbd

4 Abstract

Title

EURAS-CORA

European Active Surveillance Study Comparing Regimens of Application in combined hormonal contraception

Study protocol version of 01 August 2014

Author: [name]
Principal Investigator
[name]

Rationale and background

FC Patch Low uses the transdermal route for contraception. It is applied once a week for three consecutive weeks followed by a break of one week (21/7). One patch contains 2.1mg gestodene and 0.55mg ethinyl estradiol, which is equivalent of releasing 0.06mg gestodene and 0.013mg ethinyl estradiol per 24 hours. VTE and ATE are well-known side effects of COCs. Though the FC Patch Low is not expected to have a negative impact on the risk of VTE and ATE compared to combined oral contraceptives (COC) containing LNG, a prospective, controlled, non-interventional, long-term cohort study to assess the impact of short- and long-term risk was deemed appropriate as data on transdermal use of GSD is limited so far.

Research question and objectives

The primary objective of the study is to characterize and compare the risks of short- and long-term use of FC Patch Low with levonorgestrel-containing combined oral contraceptives (COC_{LNG})², in a study population that is representative for the actual users of the individual preparations. This includes an estimate of the absolute risk of rare serious adverse outcomes. The main clinical outcomes of interest for the short and long-term follow-up are venous thromboembolism, specifically deep venous thrombosis of the lower extremities and pulmonary embolism.

Study design

Multinational, controlled, prospective, active surveillance study that follows two cohorts. The cohorts consist of new users (starters³ and restarters⁴) of two different groups of hormonal contraceptives: FC Patch Low and COC_{LNG}. The study will use a non-interference⁵ approach to provide standardized, comprehensive, reliable information on these treatments in a routine clinical practice setting. Study participants will be enrolled via an international

² cf. Section 9.2.1

³ First ever user of a CHC

⁴ User who restarts hormonal contraceptive use with a CHC (same CHC as before or new CHC) after an intake break of at least two months.

⁵ I.e., 1) all new users of FC Patch Low or COC_{LNG} are eligible for enrollment if they give their informed consent; and 2) the physician's prescribing, diagnostic, or therapeutic decisions take place before study participants are recruited.

network of 2,000 – 3,000 CHC prescribing health care professionals. Study participants will be followed up for 24 months. All outcomes of interest will be captured by direct contacts between the investigator team and the study participants. Reported outcomes of interest will be validated via attending physicians and relevant source documents. The classification of outcomes of interest into ‘confirmed’ and ‘not confirmed’ will be verified by blinded independent adjudication.

Population

Approximately 101,000 study participants (50,500 FC Patch Low and 50,500 COC_{LNG} users) will be recruited via a network of 2000 – 3000 CHC-prescribing health care professionals (e.g. gynecologists and general practitioners) in approximately 6 European countries. All starters and restarters (see above) of FC Patch Low or COC_{LNG} who are willing to participate in the study are eligible for enrollment into the study⁶.

Variables

Primary statistical variable: VTE hazard ratio for FC Patch Low vs. COC_{LNG} adjusted for age, BMI, duration of current use and family history of VTE. Results are based on patient-reported VTE that will be validated via the attending physicians and medical records. Other variables include arterial thromboembolism, cancer, pregnancy related data, application site reactions and serious adverse events.

Data sources

This is a field study. Exposure to hormonal contraceptives, concomitant medication, primary and secondary outcomes, potential confounding factors and potential effect modifiers will be documented by the study participants as well as the recruiting and attending physicians in the questionnaires, and additional documentation sheets, if needed.

Study size

The study is sufficiently powered to show non-inferiority of FC Patch Low compared to COC_{LNG} assuming that the true VTE risk among FC Patch Low users is not higher than among COC_{LNG} users. For this purpose a total of 101,000 women (50,500 FC Patch Low and 50,500 COC_{LNG} users) will be followed up for approximately 150,000 woman-years (WY). The power calculations are based on the following parameters: 1) α of 0.05 (one-sided); 2) power (1- β) of 0.80 and 3) non-inferiority limit on hazard ratio of 1.5.

Data analysis

The final analyses will include both an “as treated” (AT) and an intention-to-treat (ITT) analysis using Cox regression models. The safety conclusions of the study, however, will be based on the AT analyses because the ITT approach potentially dilutes differences between treatments. The appropriate confounding variables will be built into the statistical models. Crude as well as adjusted hazard ratios (HRs) will be calculated. The null hypothesis to be tested is: $HR_{VTE} \geq 1.5$ (i.e., the VTE hazard ratio for FC Patch Low vs. COC_{LNG} is higher than or equal to 1.5). The alternative hypothesis is: $HR_{VTE} < 1.5$.

⁶ cf. Section 9.2.2

Milestones

Task	Planned date⁷
Start of data collection	June 2015
End of recruitment	June 2020
Last regular follow-up	June 2021
Final report of study results	December 2021

⁷ cf. Section 9.9 (“Limitations of the research methods”), last paragraph

5 Amendments and updates

None

6 Milestones

Milestone	Planned date⁸
Registration in the EU PAS register	May 2015
Start of data collection	June 2015
Interim Reports	6-monthly until end of study
End of recruitment	June 2020
Last regular follow-up	June 2021
End of data collection ⁹	September 2021
Final report of study results	December 2021

⁸ cf. Section 9.9 (“Limitations of the research methods”), last paragraph

⁹ includes 3 months of loss to follow-up activities after the last regular follow-up

7 Rationale and background

Combined oral contraceptives (COCs) became available in the early 1960s and are - with currently about 100,000,000 users worldwide – the most popular form of effective, reversible contraception available. However, alternative methods for hormone administration have been investigated and are widely used, including injections, implants and intrauterine devices. To broaden the choice of female contraceptive methods, the transdermal route through the use of a patch has been developed because of its potential benefits. With respect to compliance, a patch only has to be applied once per week (three weeks active patch plus one week break, i.e. 21/7 day cycle). This is likely to facilitate its compliant use, especially in women who find it difficult to adhere to a daily intake regimen [1].

From a pharmacological point of view, the development of a patch for hormonal contraception is based on the rationale that active substances given via a transdermal route are not subject to first pass metabolism in the liver; thus, effective serum levels can be achieved with lower total drug exposure, especially with substances of reduced oral bioavailability like ethinyl estradiol (EE). Transdermal formulations provide more stable levels of the active substances in the body, in contrast to oral preparations, which give rise to fluctuations and high peak concentrations. Furthermore, the drug delivery via the transdermal route is unaffected by gastrointestinal complaints such as vomiting and diarrhea. To date, the only contraceptive control patch available on the market is the EE and norelgestromin (NGMN) patch, approved in the US (Ortho Evra) and in Europe (Evra).

The newly developed FC Patch Low consists of a fixed combination of ethinyl estradiol (EE) and gestodene (GSD). The estrogen component, EE, is the standard estrogen used in nearly all combined OCs. It provides acceptable skin permeability and offers efficacious cycle control. The progestin component, GSD, has been extensively used in a wide variety of OCs and products for hormone therapy for over 25 years and has a well-known efficacy and safety profile. GSD was selected based on its high progestogenic potency per weight of the progestin [2] and its good skin permeability, which is unique in comparison to other progestins and renders it specifically suitable to be chosen in a patch application. In comparison to other progestins, GSD also offers particularly good cycle control.

The combination of EE and GSD is well known for many OCs marketed in the European Union (EU) and considerable experience has already been documented for this combination. Worldwide safety data for GSD are based on more than 88,000,000 women-years (WY) of exposure to GSD-containing combined OCs (as of March 2012). However, such experience and epidemiological studies only apply to oral formulations. Although the overall systemic exposure of GSD and EE is almost similar in the patch compared to the oral formulation, daily fluctuation of plasma levels with the oral administration impact the safety profile. Besides, exposure to the respective metabolites of the components may be different with both modalities of administration and this may alter the safety profile. Conclusively, safety data collected with the oral route, could not be reliably extended to the patches. Therefore,

a PASS was chosen to investigate the risk of thromboembolism with this new formulation and compare it to levonorgestrel-containing oral contraceptives. The EURAS-CORA study is part of the Risk Management Plan (RMP).

Since the year 2000 the EURAS [3] study comprehensively investigated the risk of VTE and other serious cardiovascular outcomes which might be associated with OC use. Similar comprehensive data from large, controlled, prospective studies with defined follow-up procedures of rare serious adverse events and low loss to follow-up rates are not available for a patch containing GSD and EE. Data from randomized clinical trials (including 3,570 women) did not show any serious health concerns for FC Patch Low. However, the statistical power to detect rare adverse events is limited in these studies and no firm conclusion could be drawn from the clinical trials regarding the thromboembolism risk. Therefore, it is not yet known, how the risk of FC Patch Low compares with the risk with low dose LNG-containing CHCs. Based on general public concerns about the safety of COCs the study will not only focus on VTE but also on arterial thromboembolism, cancer, pregnancy related data, application site reactions and serious adverse events. The funder has asked ZEG to conduct a large epidemiological study with a robust and efficient study design.

The EURAS study and similar studies (such as INAS-OC¹⁰ and TASC¹¹) have demonstrated that a large, prospective, controlled, long-term cohort study is suitable for (1) safety monitoring of contraceptives, (2) reliable identification of relevant clinical outcomes and (3) providing robust estimates of their incidence. The study described in this protocol has a similar design with a few modifications due to country and product-specific characteristics.

This observational study is being conducted as an imposed obligation for a post-authorization safety study described as a condition for market authorization in accordance with an Article 10a of the EU Regulation 726/2004. This study will include European women using specific contraceptives: FC Patch Low and levonorgestrel-containing oral contraceptives (COC_{LNG})¹². The objective of the study is to assess the cardiovascular and other health risks associated with short and long-term use of FC Patch Low compared with COC_{LNG} during standard clinical practice.

¹⁰ Clinicaltrials.gov identifier: NCT00335257

¹¹ Clinicaltrials.gov identifier: NCT00524771

¹² cf. Section 9.2.1

8 Research question and objectives

The primary objective of the study is to characterize and compare the risks of short (6 months and less)- and long-term use (more than 6 months) of FC Patch Low with COC_{LNG}, in a study population that is representative for the actual users of the individual preparations. This includes an estimate of the absolute risk of rare serious adverse outcomes.

The main clinical outcomes of interest for the short and long-term follow-up are venous thromboembolism (VTE), specifically:

- Deep Venous Thrombosis (DVT) of the lower extremities (ICD-10 codes: I80.1, I80.2); excluding I80.3
- Pulmonary Embolism (PE); this includes the ICD-10 codes I26.0 and I26.9

Furthermore, sensitivity analyses are planned in order to

- 1) evaluate the impact of including I80.3 (phlebitis and thrombophlebitis of lower extremities, unspecified), which means that DVT of the lower extremities plus I80.3 plus pulmonary embolisms are analyzed
- 2) all DVTs and pulmonary embolisms.

Secondary objectives of the study are to measure/describe for FC Patch Low users and compare to users of COC_{LNG} during standard clinical practice;

- All VTE, including thromboses of renal, mesenteric, portal and retinal veins¹³
- Arterial thromboembolism (ATE) incidence rate in short- and long-term users. ATE includes acute myocardial infarction (AMI) and cerebrovascular accidents (CVA)
- Cancer entities
- Application site reactions
- Serious adverse events
- Pregnancy related outcomes

¹³ ICD-10 codes: I26.0, I26.9, I63.6, I67.6, I80.1, I80.2, I80.3, I81, I82.2, I82.3, I82.8, I82.9, H34.8, K55.0 and N28.0

9 Research methods

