The following information will be recorded at the baseline visit after the study participant has provided written informed consent: prescribed hormonal contraceptive, user status (starter/restarter), risk factors (e.g. personal and family history of VTE and ATE, age, BMI), demographic and medical history, including medication history, history and duration of use of hormonal contraceptives and previous participation in studies (e.g. clinical or observational studies). Additionally, information will be collected on the receipt of the patient information card (study participants will be asked at baseline and follow-up) and the checklist for prescribers (physicians will be asked at baseline). Study participants will also give their contact details like addresses, e-mail addresses and phone numbers, those of their relatives or friends, and the primary care physician. Names, addresses and phone numbers are to be documented on a separate sheet, in compliance with data protection regulations.

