During this study, information on known risk factors for VTE will be collected. This includes age, BMI, family history of VTE and current duration of use. Information on the smoking status (current, ever, never, number of cigarettes and period of smoking) and socio-economic status (highest level of education) will be collected as well although they are believed to have a minor influence. All potential confounding factors will be included in a multivariable model to test whether they change the strength of the association between exposure and outcome.

The main clinical outcomes of interest for the short (FU 1 after 6 months) and long-term follow-up (FU 2 after 12 months and FU 3 after 24 months) are venous thromboembolism (VTE), specifically:

- Deep Venous Thrombosis (DVT) of the lower extremities (ICD-10 codes: I80.1, I80.2); excluding I80.3
- Pulmonary Embolism (PE); this includes the ICD-10 codes I26.0 and I26.9

Furthermore, sensitivity analyses are planned in order to

- 1) evaluate the impact of including I80.3 (phlebitis and thrombophlebitis of lower extremities, unspecified), which means that DVT of the lower extremities plus I80.3 plus pulmonary embolisms are analyzed
- 2) all DVTs and pulmonary embolisms.

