9.7 Data analysis

Based on available data and pharmacological considerations the *a priori* assumption is that use of FC Patch Low is not associated with an increased risk of VTE compared to COC_{LNG}. That is, a statistical comparison of FC Patch Low and COC_{LNG} is not expected to show a difference. Therefore, a non-inferiority design was chosen to investigate the VTE risk of FC Patch Low. The primary analysis will be based on the comparison of the upper confidence limit for the point estimate of the VTE²² hazard ratio with the predefined non-inferiority limit (see below).

The final analyses will include both an “as treated” (AT) and an intention-to-treat (ITT) analysis using Cox regression models. The safety conclusions of the study, however, will be based on the AT analyses (outcomes of interest will be assigned to the treatment she used at the time of the event) because the ITT approach (outcomes of interest are assigned to the treatment which was prescribed at study entry) potentially dilutes differences between treatments.

Incidence rates, incidence rate ratios (HRs), excess risks, as well as crude and adjusted hazard ratios will be calculated. The appropriate confounding variables will be built into the model. Based on the expectation of a small absolute number of serious outcomes of interest the number of confounding variables will be limited to well-established risk factors for these outcomes (e.g., age, BMI, duration of current use, and VTE history). The final decision on the confounding variables will be made by the Safety Monitoring and Advisory Council before the first interim analysis of follow-up data. In addition, alternative analysis will be performed with other potential baseline risks to check the appropriateness of this decision. Similar analyses will be performed for all VTE (cf. Section 8) and arterial thromboembolism (e.g., acute myocardial infarction and stroke), the other secondary variables and other serious adverse events.

The null hypothesis to be tested is: $HR_{VTE} \geq 1.5$ (i.e., the VTE hazard ratio for FC Patch Low vs. COC_{LNG} is higher than or equal to 1.5). The alternative hypothesis is: $HR_{VTE} < 1.5$.

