This study combines several methodological strengths that are substantial for the validity of the results: i) prospective, comparative cohort design; ii) availability of important confounder information (e.g., BMI and family history of VTE); iii) validation of outcomes of interest and the exposure of the relevant cases; iv) comprehensive follow-up procedure and very low loss to follow-up to minimize underreporting; v) independent, blinded adjudication of VTE cases; vi) relevant statistical analyses (e.g., stratified analyses by user status and exposure period; comparison of isochronous, new user cohorts; sensitivity analyses on the impact of the adjudication process, outcome definition, and prognostic factor/covariate selection); vii) study population representative for oral contraceptive users under routine clinical conditions; viii) generalizability of results as hormonal contraceptive use in this study reflects routine clinical use and study participation is not limited by medical inclusion and exclusion criteria; ix) supervision by an independent Safety Monitoring and Advisory Council, and scientific independence from the study funder.

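### The primary VTE hazard ratio is not adjusted for starter/restarter status, and the protocol does not say consistently which VTE history it is adjusted for

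*Protocol*

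**What the plan says.** **Covariates.** Section 4 (Abstract, Variables) defines the primary variable as the VTE hazard ratio "adjusted for age, BMI, duration of current use and family history of VTE". Section 9.3.1, on known risk factors to be collected, agrees: "This includes age, BMI, family history of VTE and current duration of use". Section 9.7 limits the model to well-established risk factors and illustrates them with a list, "e.g., age, BMI, duration of current use, and VTE history". It then adds: "The final decision on the confounding variables will be made by the Safety Monitoring and Advisory Council before the first interim analysis of follow-up data".

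**Data collected.** The baseline items in Section 9.2.3 include "user status (starter/restarter), risk factors (e.g. personal and family history of VTE and ATE, age, BMI". Personal history, family history and user status are therefore all available. Section 9.2.2 names the conditions that exclude a woman from the VTE analysis: recent pregnancy, a history of cancer or chemotherapy, and increased genetic VTE risk. Personal history of VTE is not among them.

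**User status.** Section 4 states: "The cohorts consist of new users (starters³ and restarters⁴) of two different groups of hormonal contraceptives". A restarter is a woman who resumes hormonal contraception "after an intake break of at least two months". Under Section 9.2.2, each patch user recruited is followed by the next willing new user of the comparator, whether starter or restarter. Section 9.9 counts "stratified analyses by user status and exposure period" among the study's strengths.

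**The concern.** Non-inferiority is decided by one number: the upper confidence limit of the primary hazard ratio against 1.5. What enters that model matters more than what enters supporting analyses, and the protocol is weak here in two respects.

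First, the VTE history covariate has two wordings that can mean different variables. Section 9.9 relies on family history to offset the lack of genetic data. Read literally, Section 9.7 could replace it with personal history or merge the two. How the primary model treats women with a previous VTE is also left unclear, since they are neither excluded nor covered by the Abstract's list.

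Second, a cohort that mixes first-ever users with restarters can differ between treatments in that mix. If VTE risk also differs by user status, the primary hazard ratio is confounded. Duration of current use may look as if it covers this, but a starter and a restarter who both began a month ago have the same duration.

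**Working it through.** **1. The plan's own figure.** Section 9.5 gives 150 events for a limit of 1.5, a true hazard ratio of 1.0, one-sided α of 0.05, power of 0.80 and 1:1 cohorts. By Schoenfeld's formula:

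events = 4(1.645 + 0.842)² / (ln 1.5)² = 150.4

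Power at 150 events is 79.9%. The figure reproduces, and nothing below changes it.

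**2. The covariate lists side by side.**

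| Place | VTE history item | User status | Standing |
|---|---|---|---|
| Section 4, Variables | family | absent | stated as the definition of the primary variable |
| Section 9.3.1 | family | absent | known risk factors to be collected |
| Section 9.7 | not specified | absent | illustrative; the Council decides |
| Section 9.2.3 | personal and family, both recorded | recorded | baseline data |

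**3. What duration of current use can control.** Every participant begins an episode of use at about study entry. Table 1 leaves the time of within-study switchers out of counted exposure; with loss to follow-up, this is an 11% deduction. For most counted time, duration is therefore close to time since entry. If time since entry is the Cox time axis (the protocol does not state the axis), duration is nearly constant within each risk set and cancels from the partial likelihood. On any axis, it does not separate a first-ever user from a restarter at the same point in the episode.

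**4. Size of the possible bias.** Let p₁ and p₀ be the starter shares in the patch and comparator cohorts, and R the starter-to-restarter VTE risk ratio. All three are assumptions. With R constant over follow-up, the hazard ratio without user status is multiplied by

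b = [1 + p₁(R − 1)] / [1 + p₀(R − 1)].

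With SE(log HR) = √(4/150) = 0.1633:

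- false non-inferiority at a true hazard ratio of 1.5 = Φ(−ln b / 0.1633 − 1.645)
- power at a true hazard ratio of 1.0 = Φ((ln 1.5 − ln b) / 0.1633 − 1.645)

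| p₁ / p₀ | R | b | False non-inferiority | Power |
|---|---|---|---|---|
| equal shares | any | 1.00 | 5% | 80% |
| 30% / 40% | 1.5 | 1.15/1.20 = 0.958 | 8.3% | 86% |
| 30% / 40% | 2.0 | 1.30/1.40 = 0.929 | 11.7% | 90% |
| 40% / 30% | 1.5 | 1.20/1.15 = 1.043 | 2.8% | 72% |
| 40% / 30% | 2.0 | 1.40/1.30 = 1.077 | 1.8% | 65% |

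A wider split of 20% / 40% gives b = 0.917 to 0.857 and false non-inferiority of 13% to 24%. The same split reversed gives b = 1.09 to 1.17, and power of 62% to 46%. None of these figures allows for age adjustment.

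**5. Check by simulation.** In a simulated new-user cohort with true hazard ratio 1.0, starter shares of 30% and 50%, and R = 2, the mean Cox hazard ratio over six runs of about 1,490 events was 0.87 without user status and 1.01 with it. The formula gives 1.30/1.50 = 0.87.

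**The case against.** The strongest reply is that the covariate set is not final. Section 9.7 offers examples and leaves the decision to the Council before the first interim analysis. Section 9.3.1 has all potential confounders tested in a multivariable model, Section 9.7 adds alternative analyses with other baseline risks, and Section 9.9 plans stratification by user status. An imbalance would be seen and examined. This stands as far as it goes: user status is not ignored. But the Abstract states the set as the definition of the primary variable, and supporting analyses do not alter the one confidence limit that decides non-inferiority.

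It can also be said that Section 9.7 is merely shorthand for family history, since Sections 4, 9.3.1 and 9.9 all say family. That is the likelier reading. The text does not confirm it, and personal history remains unassigned either way.

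Three stronger readings are tempting, and the documents do not support them.

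- **That adjusting for duration of current use is an error.** The time axis is not stated and may properly be left to the SAP. Women who stop and restart would have a duration different from time since entry, and Section 9.7 plans time-dependent factors. A redundant term does no harm.
- **That the plan is biased towards non-inferiority.** No starter shares are given, nor any risk by user status, so the direction is unknown.
- **That the false non-inferiority rate is 13–24%.** This needs an assumed 20% / 40% split in one direction, a risk ratio of 1.5 to 2 throughout follow-up, and no correction through age. If starters' excess risk were confined to the early months, the effect would be smaller.

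**Conclusion.** The point holds as a matter of specification. The protocol names the VTE history covariate in two ways that can mean different variables, and it does not commit starter/restarter status to the primary model, although the variable is recorded, is unmatched and is considered worth stratifying by.

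Bias arises only if starter shares differ between cohorts and VTE risk differs by user status. Under the moderate assumption of a ten-point difference in starter share and a risk ratio of 1.5 to 2, the primary hazard ratio shifts by about 4–7% downwards (false non-inferiority about 8–12% instead of 5%) or 4–8% upwards (power about 72–65% instead of 80%), depending on which cohort has more starters. Age adjustment would remove some of this; how much cannot be derived from the documents. With equal shares there is no bias. The change should be made because the possible effect on a 1.5 limit is not negligible and the remedy costs almost nothing.

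**What to change.** Add starter/restarter status to the primary Cox model, as a stratum or a covariate; either removes the gap.

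Use one identical covariate list in Sections 4, 9.3.1 and 9.7. It should name family history of VTE and, as a separate item, personal history of VTE. If the Council is to keep the final decision on covariates, the Abstract should say so, and the Council should start from this list.

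The cost is wording in the protocol, carried into the SAP, before the Council fixes the covariates. Every variable is already collected at baseline, one or two more terms are easily supported by about 150 events, and the event target stays as it is. This point requires neither a change of Cox time scale nor stratification by country.
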